3.12 Ethical consideration

Ethical approval will be provided from institutional ethics review. Consent form would be presented by investigator for each subject before experimental trial. Subject will require reading and signing.

[figure not shown]
To confirm confidentiality of participant information, each participant will get a unique alphanumeric code. The information will only be shared between the researchers.

There is no payment and transportation provide to participants.

3.13 Limitation and strength

Randomly involved of subject into intervention groups is one of strength in our study. One of limitation is subject and observer could not be blind.

4. Devices and setting figure

[figure not shown]
Name	Picture
a) High volume suction	
b) Low volume suction	
All in one system (dry-shield)	
Extra oral suction	
Microbial air sampler device (sampl'air ASE)	

**Digital dust monitor , KANOMAX , model
3443,**

**Circles represent location of microbial air
sampler device**

**Square represents digital dust monitor
device**

5. References

2. Garner JS. Guideline for isolation precautions in hospitals. The Hospital Infection Control Practices Advisory Committee. *Infection control and hospital epidemiology*. 1996;17(1):53-80.

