3.4 Study area and setting

1. This study will be conducted in close rooms at educational hospital, public hospital and private dental clinic. Humidity and temperature will be recorded at the beginning, measuring particles oral bacteria and fungus will be performed 15 minutes before and approximately 15 minutes during scaling and prophylaxes procedure in two opposite quadrants in left side. Additionally 5 minutes will require between two interval to allow cleaning process of filter in Digital dust monitor. Microbial sampler devices will be distributed at several locations in room, three microbial air sampler devices around patient, at 8 o'clock position, 1 o'clock position and 4 o'clock. Another device that will be placed near to air condition and one agar media on the floor to control another microbial agents that could be arising from A.C.. Intervention devices that will be used is EOS where being place on left side of patent to allow comfortable movement of hygienist and suction cone will be away from patient mouth from 10 -15 cm based on manufacture instruction.

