3.10 Variables and Data collection

Measurement devices

2. Digital dust monitor

Particles matter will be measured using Digital dust monitor (model 3443, KANOMAX.USA INC., made in Japan). This device measure particle size that range from 0.1 to 10 Mm using light scattering method (semiconductor laser radiation light source) with flow rate 1 L/min. air is collect through a filter which is built-in in order to eliminate coarse particles. Filter is reusable and it needs approximately 5 minutes cleaning time depending on environment. Minimum, maximum, and average concentration result show among measurement time. Calibration of device will be performed according to manufacture instruction.

3. Microbial air sampler device (sampl'air ASE)

Is considered as active air sampler method which used to collect microorganism onto solid media with flow rate 100 L/ min. Positive hole conversion table should be used in order to counting colony; colony forming units per volume of air (CFU m⁻³).

In this study a specific agar media will be used to collect oral bacteria and fungus.

Outcome variable

Particle count level (difference in PN count[ΔPN ;post-test – pre-test , counts/ m³])
(continuous variable)

Average of oral bacterial concentration before and during procedure

Average of fungus concentration before and during procedure

Microbial air concentration including bacteria and fungus before and during procedure (floor and near to A.C)

Explanatory variable

Categorical variable

Place ,intervention groups, order of patient ,gender and supragingival calculus (mild, moderate, heavy) ,

Continuous variable

time of procedure that staring from the beginning of scaling until finishing of scaling (in minutes), time on day (morning, afternoon), age, year experience of hygienist, distance of room, humidity, and room temperature.

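### Colony counting is not masked: section 3.13 accepts an unblinded observer for every outcome, so observer bias in the bacterial and fungal counts is not prevented although it could be

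*Combined protocol and SAP*

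**What the plan says.** Section 3.13 gives the plan's only statement on blinding: "One of limitation is subject and observer could not be blind". It does not say who the observer is. It also does not separate work in the room from the later handling of samples.

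Section 3.10 lists four outcomes. The particle outcome comes from an instrument display: "Minimum, maximum, and average concentration result show among measurement time". The others are microbial: "Average of oral bacterial concentration before and during procedure", "Average of fungus concentration before and during procedure", and a microbial air concentration at the floor and near the air conditioner. Organisms are collected on solid media, and on the count the section says: "Positive hole conversion table should be used in order to counting colony". It does not say who counts, where, when, or with what knowledge of the group or time point.

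Section 3.4 places "three microbial air sampler devices around patient", plus one near the air conditioner and one agar plate on the floor. The last two are there to account for organisms coming from the air conditioning.

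Section 3.12 says that "each participant will get a unique alphanumeric code". The purpose given is confidentiality. It adds: "The information will only be shared between the researchers". Nobody is named as kept from the allocation.

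**The concern.** The limitation in 3.13 is wider than the design requires. The patient and the hygienist cannot fail to see an extra-oral unit or a dryshield mouthpiece. An agar plate carries no sign of the device unless its label or its reader's memory supplies one.

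A colony count is made by a person and leaves some room for judgement. A reader who knows that a plate came from a device session, or from the period during scaling rather than before it, could read it differently. Section 3.11 tests both contrasts: groups by ANOVA, and before versus during by a paired t test. No planned analysis would detect or remove a reading bias, because the plan has no duplicate counts and no masked subset for comparison. If the bias favoured the newer devices, it would look like a treatment effect.

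**Working it through.** **1. Is masking provided anywhere?** Set side by side, the sections leave a gap:

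- 3.13 accepts an unblinded observer and makes no exception.
- 3.10 describes the count but not the counter.
- 3.12 gives one code per participant and shares the information among the researchers.
- No section mentions masked plate labels, a reader without the allocation, or duplicate counts.

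**2. Would the planned participant code be enough?** Section 3.4 gives 3 samplers around the patient + 1 near the air conditioner + 1 floor plate = 5 sampling points. Section 3.10 has them measured before and during, so 5 × 2 = 10 plates per participant per medium. With 120 participants (3.7) that is 10 × 120 = 1,200 plates per medium, or 2,400 if bacteria and fungi use separate plates (an assumption). One code per participant cannot identify a plate, and it does not hide the group from researchers who share the information. Plate-level codes are needed.

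**3. How sensitive is a comparison to biased reading?** The plan gives no figure on counting error, SD or blinding, so there is nothing of its own to reproduce. The inputs are:

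- Alpha 0.05 (3.11). Two-sided is an assumption.
- 30 per group = 120 / 4, assuming an equal split. Section 3.8 can be read as 40 per group, which would make 160 and conflicts with 3.7.
- True effect zero (assumption).
- Under-reading of device plates by a fraction b, and SD s of the analysed value on the log scale (both assumptions).

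Formula: two-sided t test on 58 degrees of freedom, with noncentrality = −ln(1 − b) / (s × √(2/30)).

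For b = 0.10 and s = 0.5: −ln(0.90) = 0.105; √(2/30) = 0.258; noncentrality = 0.105 / (0.5 × 0.258) = 0.82. The false-positive rate is 12.6%.

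| Log SD | b = 10% | b = 20% |
|---|---|---|
| 0.4 | 17.1% | 56.5% |
| 0.5 | 12.6% | 39.8% |
| 0.7 | 8.8% | 22.9% |
| 1.0 | 6.9% | 13.6% |

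With b = 0 the rate is 5%. With b = 5% and SD 0.5 it is 6.8%. A normal approximation agrees: a shift of 0.2 SD gives 12.1% with 30 per group and 14.6% with 40.

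**4. When do these figures apply?** If every plate from a device patient is under-read by the same fraction, then on the log scale ln[(1 − b) × during] − ln[(1 − b) × before] = ln(during) − ln(before), and the bias cancels. The table therefore needs under-reading that differs between before and during plates, or an analysis that ignores baseline. Section 3.11 specifies no log transformation, so the table is not a model of the planned test.

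**The case against.** The strongest reply is that this is silence, not a demonstrated defect. The observer in 3.13 may be only the person in the room, for whom the limitation is right, and a laboratory colleague who never sees the allocation may already count the plates. This stands as far as it goes. A reader might infer that observer bias does enter the microbial outcomes; the documents do not support that, because they do not identify the counter. But 3.13 is a stated position without exception, and nothing elsewhere narrows it.

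Second, the room for judgement is limited: 3.10 specifies selective media and a conversion table. This is partly right. Selective media narrow the question of what counts as oral growth. The table adjusts a count once it has been made and does not protect the count itself. How much judgement remains is not documented.

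Third, a reader might infer that three of the four outcomes are equally exposed, or that the participant codes already provide masking at almost no cost. Neither holds. The floor and air-conditioner plates serve mainly as controls, and the particle outcome, which is listed first and is the only one with a regression model, is read by an instrument. The codes serve confidentiality, are one per participant, and do not mask by themselves.

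Fourth, the false-positive figures rest on assumed inputs. This stands in full, and they should not be read as an estimate of bias in this trial.

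**Conclusion.** The point holds in a limited form. The plan accepts an unblinded observer for every outcome and provides no masking of colony counts, although counting can be separated from the room. Bias in the bacterial and fungal outcomes, and in the control measure, is not prevented; the documents do not show that it is present.

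Its size is unknown. For 10% under-reading the illustrative false-positive rate is about 7% to 17% against a nominal 5%, under the assumptions and the condition on before and during plates set out above. Masked counting would leave unblinded conduct in the room, such as sampler placement and procedure time, untouched. The change is worth making because it removes an avoidable weakness and needs no new visit, procedure or sample.

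**What to change.** In 3.10, state who counts the plates, and add that:

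- each plate carries a neutral random plate code that shows neither group nor period, applied by an existing team member who does not count;
- the code list and the allocation are kept from the reader;
- plates are read in mixed order across groups and periods where incubation timing allows;
- counts are locked before codes are linked to groups.

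In 3.13, confine the limitation to the subject and the people in the room. If reading is already masked, a sentence saying so settles the point.

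The cost is relabelling about 10 plates per participant per medium (some 1,200 per medium in all) and some batching. The plan gives no reading timetable, so how far plates from different sites can be mixed has to be settled locally. No extra reader is needed if existing team members divide coding and counting; a counter who attended the sessions or holds the code list would not be masked by relabelling alone.
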